### 11.4 Deaths

All deaths within the trial (whether considered a SAE or not) will be reported to the Chief Investigator and the Sponsor using the relevant Death Form. Deaths occurring in the maintenance phase will be documented and reported separately to SAEs.

Total number of deaths per site will be reported in accordance with section 9 using

the full analysis population. Additionally the following causes of death will be summarised:

All causes of death that apply:

- Infection
- Active vasculitis
- Pulmonary embolus
- Withdrawal of renal replacement therapy
- Acute myocardial infarction
- Sudden death (cause unknown)
- Cerebrovascular disease
- Cancer
- Unknown
- Other

Missing data will be treated as cause of death not applicable.

## 11.5 Pregnancies

Pregnancy or inadequate contraception in women of childbearing potential forms one of the exclusion criteria for the study. A pregnancy test was performed at baseline for all women of childbearing potential to assess eligibility. Data was retained for safety and will not be reported.

All pregnancies within the trial (either the trial participant or the participant's partner) will be reported to the Chief Investigator and the Sponsor using the relevant Pregnancy Reporting Form within 24 hours of notification. Pregnancy is not considered an adverse event (AE) unless a negative or consequential outcome is recorded for the mother or child/foetus. If the outcome meets serious criteria, this would be considered an SAE. Data from the Pregnancy Reporting Form of all pregnancies occurring in the maintenance phase will be reported as listings sorted by site.

## 11.6 Clinical Laboratory Evaluations

Clinical laboratory tests will be performed at baseline (either at Screening or Month 0, taking the latest value if assessment were performed at both visits), and at each visit in the maintenance phase (months 4, 8, 12, 16, 20, 24, 27, 30, 36, 42 and 48). Measured values will be recorded in the Clinical Laboratory Tests Forms and entered

in the MACRO database. Data management will ensure that any missing values are due to the test not being performed (“Not measured” tick-box).

The following variables will be summarised in accordance with section 9 using the full analysis population. Missing values will be assumed to be “not measured” without cross-referencing the relevant tick-box.

- Clinical Labs
  - Haemoglobin (g/dL)
  - Platelets (cells x 10^9/L)
  - WBC (cells x 10^9/L)
  - ESR (mm/h)
  - Creatinine (µmol/L)
  - CRP (mg/L)
  - ALT (U/L)
  - AST (U/L)
- ANCA
  - Anti-PR3 (positive/negative)
  - Anti-MPO (positive/negative)
  - ANCA status – derived variable, details in section 1.1
- Lymphocyte markers
  - CD19 (cells x 10^9/L and %)
- Immunoglobulins
  - IgG (g/L)
  - IgM (g/L)
  - IgA (g/L)

Table 8 lists the preferred unit for reporting and the multiplicative conversion factor (CF) employed for those clinical labs collected in the CRF using different measurement units.

---

 Conversion factors taken from <http://www.scymed.com/en/smnxfd/smnxfdac.htm>

Table 8: Conversion factors

Variable	Original unit	CF	Reporting unit
Haemoglobin	g/L	0.1	g/dL
Haemoglobin	mmol/L	1.611344	g/dL
WBC	cells x 10  /mm 	1	cells x 10  /L
Creatinine	g/dL	88.42 x 10 	µmol/L
Creatinine	mg/dL	88.42	µmol/L
CRP	mg/dL	10	mg/L
CD19	cells x 10  /mm 	1	cells x 10  /L
CD19	cells/µL	0.001	cells x 10  /L
IgG	mg/dL	0.01	g/L
IgM	mg/dL	0.01	g/L
IgA	mg/dL	0.01	g/L

Laboratory values outside the ranges detailed in Table 8 will be considered un-physiological, and will be considered outliers and excluded from the analysis. All such values will be listed in a separate table (grouped by item, subject, and visit) and queried by the data manager.

Table 9: Physiological ranges for laboratory tests

Variable	Minimum	Maximum	Reporting unit
Haemoglobin	5	20	g/dL
Platelets	5	900	cells x 10  /L
WBC	1	40	cells x 10  /L
ESR	0	200	mm/h
Creatinine	30	1500	µmol/L
CRP	0	600	mg/L
ALT	0	1000	U/L
AST	0	1000	U/L
CD19	0	5	cells x 10  /L
CD19	0	100	%
IgG	0	25	g/L
IgM	0	8	g/L
IgA	0	8	g/L

Values reported with a < or > sign will not be included in the analysis, except for measurements reported within the lower bounds specified in Table 10: these will be censored to “0” and included in the analysis accordingly. Excluded values will be listed in a separate table (grouped by item, subject, and visit). A table will report the number of censored values, grouped by item, subject, and visit.

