#### 11.1.6 Dosage Modifications

Rituximab will be administered at a dose of  $375\text{mg}/\text{m}^2 \times 4$ , at weekly intervals during the induction phase of the trial. Patients achieving remission and randomised to the rituximab remission maintenance group will receive rituximab 1000mg, at months 4, 8, 12, 16 and 20. The dose of rituximab does not need to be adjusted for renal function.

If the IgG level falls below 3g/l, it should be repeated in the month prior to the next scheduled dose of rituximab and the dose not administered if the IgG level remains  $<3\text{g}/\text{l}$ . If the IgG level has risen and is  $\geq 3\text{g}/\text{l}$ , then rituximab should be administered as per protocol. For those with an IgG level remaining  $< 3\text{g}/\text{l}$ , the IgG level is checked again within the month prior to the next scheduled dose of rituximab and this dose only given if the level has risen to  $\geq 3\text{g}/\text{l}$ . IgM and IgA levels are ignored for the purpose of rituximab dosing. Dosing of azathioprine (methotrexate and mycophenolate mofetil) should continue according to protocol regardless of IgG level.

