## 9 Summary of Study Data

All continuous variables will be summarised using the following descriptive statistics: n (non-missing sample size), mean, standard deviation, median, maximum and minimum. The frequency and percentages (based on the non-missing sample size) of observed levels will be reported for all categorical measures. Summary tables will be structured with a column for each treatment arm ("Azathioprine", "Rituximab"), as well as a total column. Additionally some summary tables (e.g. baseline demographic) will also be presented split by induction regimen ("1A", "1B"). All tables will be annotated with the total population size relevant to that table/treatment, including any missing observations. In general, where appropriate, data will be listed sorted by site, subject and visit.

Only deviations from the general overview will be noted in the subsequent sub-sections within section 9.

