Figure 29: Forest plot of cox proportional hazards model – Tertiary endpoint.

Figure 30: Serious Adverse Events, forest plot of frequency and relative risk by treatment arm.

Figure 31: Non–serious infections, forest plot of frequency and relative risk by treatment arm.

Figure 32: Kaplan–Meier plot of SAE–free survival by treatment arm.

Figure 33–45: Boxplots by treatment arm of continuous clinical lab tests:  
Haemoglobin, Platelets, WBC, ESR, Creatinine, CRP, ALT, AST, CD19, CD19 (%), IgG, IgM, and IgA.

Figure 46–48: Stacked bar charts by treatment arm of discrete clinical lab tests:  
Anti–PR3, Anti–MPO, and ANCA status.

Figure 49: Alluvial plot of ANCA status by treatment arm, showing change from month 4 to month 24 and to month 36.

Figure 50: Bar charts of EQ–5D–5L questionnaire item's responses.

Figure 51: Boxplot of EQ–5D–5L index totals (VAS Health state, OTT utility score, and VAS utility score) by treatment arm.

Figure 52–54: Bar charts of PROMIS questionnaire item's responses (fatigue, pain, physical ability).

Figure 55: Bar chart of PROMIS questionnaire sub–totals by treatment arm.

Figure 56: Boxplots of PROMIS questionnaire sub–totals by treatment arm.

Figure 57: Boxplot of PROMIS questionnaire total score by treatment arm.

Figure 58–63: Bar charts of SF–36 questionnaire item's responses.

Figure 64: Boxplot of SF–36 questionnaire sub–totals by treatment arm.

Figure 65: Boxplot of SF-36 questionnaire PCS and MCS components by treatment arm.

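### SAP 11.6 sets Table 10 results marked '<' to zero and excludes every other '<' or '>' result, which biases the descriptive laboratory summaries and can distort the arm contrast

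*SAP*

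**What the plan says.** SAP 11.6 gives a general rule: "Values reported with a < or > sign will not be included in the analysis". It allows one exception, "except for measurements reported within the lower bounds specified in Table 10: these will be censored to" zero and then analysed. Table 10 has five rows: CRP <5 mg/L, CD19 <1%, CD19 <0.02 x 10^9/L, IgM <0.3 g/L and IgA <0.3 g/L. IgG is not among them, and no row carries a '>' sign.

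The SAP discloses part of what it does. Excluded values go into a separate listing, and "A table will report the number of censored values, grouped by item, subject, and visit". It gives no by-arm percentage and no sensitivity analysis for the substitution.

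The affected outputs are the SAP section 9 summaries ("n (non-missing sample size), mean, standard deviation, median, maximum and minimum") and, in section 13, "Boxplots by treatment arm of continuous clinical lab tests". Table 9 accepts IgM and IgA from 0 to 8 g/L, so a measured IgM of 0.20 g/L stays in and a substituted zero is not flagged as out of range. Table 9 also accepts ESR up to 200 mm/h.

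**The concern.** The rule has three faults.

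1. **Zero is the lowest value available.** The error therefore always runs the same way, and it is larger in the arm and at the visit with more below-bound results.
2. **Signed and measured results are treated differently.** A true IgM of 0.29 reported as '<0.3' becomes 0 and ranks below a measured 0.10 from a laboratory with a lower limit. SAP 8.8 plans about 50 to 60 centres, and Table 8 shows results arriving in different units, so differing reporting limits are plausible.
3. **Exclusion depends on the value itself.** A '>' result is dropped because it is high, and a '<' result outside Table 10 because it is low. An ESR reported as '>120' would be dropped, although a measured 150 would be kept.

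At stake is the descriptive safety picture. Long-term safety of rituximab is a secondary objective (SAP 5.1.2), and IgM, IgA and CD19 by arm are part of what a reader will look at.

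**Working it through.** The plan states no figure to reproduce, so the check is the size of the substitution error.

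**Inputs from the documents.** Bound L = 0.3 g/L for IgM and IgA, and 5 mg/L for CRP (Table 10); substituted value 0 (SAP 11.6).

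**Inputs assumed.** The share of results below the bound and the shape of the distributions are not in the documents. The illustrations use lognormal values and suppose that every laboratory reports '<L' below the bound.

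**Identity.** If a share p of an arm's results is set to 0, and the true mean of those results is m (0 < m < L), the arm mean moves by −p × m. The arm difference is widened by p_R × m_R − p_A × m_A, where R is the arm with more low values and A is the other.

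- p = 20% v 10%, m from 0.1 to 0.3: (0.20 − 0.10) × m = 0.01 to 0.03 g/L.
- p = 60% v 10%, m = 0.2: 0.12 − 0.02 = 0.10 g/L; the ceiling at m = 0.3 is 0.15 g/L.

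**Lognormal IgM, closed form.** The true arm mean is exp(ln(median) + s²/2), with s the SD of the log. With d = (ln L − ln(median))/s, the share below the bound is Φ(d) and the mean after zeroing is the true mean × (1 − Φ(d − s)).

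| Medians R v A (g/L) | s | Below bound R v A | True difference | Zero rule | Error | Half the bound |
|---|---|---|---|---|---|---|
| 0.28 v 0.60 | 0.7 | 54% v 16% | −0.409 | −0.472 | +15% | −0.415 |
| 0.35 v 0.70 | 0.7 | 41% v 11% | −0.447 | −0.502 | +12% | −0.457 |
| 0.30 v 0.50 | 0.5 | 50% v 15% | −0.227 | −0.295 | +30% | −0.243 |
| 0.30 v 0.50 | 0.7 | 50% v 23% | −0.256 | −0.299 | +17% | −0.259 |
| 0.22 v 0.50 | 0.5 | 73% v 15% | −0.317 | −0.418 | +32% | −0.331 |
| 0.22 v 0.50 | 0.7 | 67% v 23% | −0.358 | −0.421 | +18% | −0.355 |

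In the first row, arm R loses 0.539 × 0.182 = 0.098 and arm A loses 0.161 × 0.217 = 0.035. The gap widens by 0.063, and 0.063/0.409 = 15%.

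**Medians and boxplots.** Zeroing does not move a below-bound value past the bound, so the median is unchanged while fewer than half the results lie below it. From half upwards the reported median can be 0 instead of a value between 0 and 0.3. In the first row the R median goes from 0.28 to 0; in the second both medians are unaffected. By the same reasoning the lower edge of a box can reach 0 once a quarter of results are below the bound.

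**IgA.** With assumed medians of 1.2 v 1.5 g/L and s = 0.7, 2.4% v 1.1% are below the bound, and the mean difference is 0.386 instead of 0.383 g/L.

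**CRP.** With s = 1.0 and a median of 2.5 mg/L, 76% are below 5 and the mean falls from 4.12 to 2.56 (−38%). With a median of 3.5, 64% are below and the mean falls from 5.77 to 4.27 (−26%). The median becomes 0 in both cases.

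**Exclusion instead of zeroing.** This is what happens to '<' results outside Table 10, and it errs the other way. If the IgM results in the two 0.30 v 0.50 scenarios were excluded, the difference would be 0.156 (s = 0.5) or 0.188 (s = 0.7) instead of 0.227 or 0.256, about 31% or 27% too small.

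**The case against.** The strongest reply is that nothing inferential rests on these summaries. That stands. Relapse is defined on BVAS/WG, hypogammaglobulinaemia on IgG (SAP 11.3), and Protocol 11.1.6 states that "IgM and IgA levels are ignored for the purpose of rituximab dosing". SAP 9.2 defines no change variable for IgM or IgA, and SAP 5.2.3 does not plan the exploratory immunoglobulin correlation.

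A reader might infer that the rule exaggerates the immunoglobulin fall under rituximab. The documents do not establish that. They give no below-bound shares. The protocol's background says that rituximab does not directly affect immunoglobulin levels, and that six-monthly re-treatment in the pilot cohort brought no significant fall. Both arms receive rituximab induction, so low values may already be common at month 4. More low IgM in the rituximab arm is plausible, but it is an assumption.

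A reader might also infer that dropping '>' results hides inflammation in the arm with more relapses. SAP 6.4 already keeps unscheduled assessments, including those at relapse, out of the scheduled-visit summaries, so the argument could reach scheduled visits only. The documents show no '>' result, and no size can be given.

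Finally, the SAP lists the excluded values and counts the zeroed ones. This discloses the problem, but the means, extremes and boxplots remain as the rule makes them.

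**Conclusion.** The concern holds as a minor point about descriptive output. For CRP, CD19, IgM and IgA, a '<' result within Table 10 is given the most extreme value possible while measured values below the same bound are kept. All '>' results and all other '<' results, IgG included, are left out because of their value.

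Means, SDs, minima and maxima are biased. The median also changes when about half or more of the results are below the bound. The arm contrast is distorted whenever p × m differs between arms, and in practice whenever the below-bound shares differ.

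The overstatement of the IgM mean difference is roughly 12 to 30% (32% in the most extreme of six scenarios). That range rests on assumed lognormal distributions and on all laboratories reporting '<0.3'; the true size cannot be computed from the documents. IgA is likely negligible. The primary analysis, the IgG <5 g/L threshold and rituximab dosing do not use the zero substitution.

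**What to change.** Reword SAP 11.6 as follows.

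- Replace zero with half of the limit actually reported for that result. The Table 10 bound should not be halved for everyone: 0.15 would exceed the known maximum of an IgM reported as '<0.1'.
- Keep measured numeric values as they are, including those below a Table 10 bound.
- Apply the same rule to '<' results outside Table 10, including IgG.
- Set a '>U' result to U instead of excluding it.
- Report the number and percentage of '<' and '>' results by arm and visit.
- Show a median as '<limit' when it falls among censored values, and mark the bound on the boxplots.

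In the six IgM scenarios above, half the limit leaves an error in the mean difference of between −1% and +7%. For the two CRP examples the mean is 8% and 2% too high.

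The cost is SAP wording and a few lines of code, with no new data. Two small drawbacks remain: means still rest on a simple substitution, and setting '>U' to U still slightly understates high values.

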**Table 10: Lower bounds of clinical labs measurements**

Variable	Sign	Value	Unit
CRP	<	5	mg/L
CD19	<	1	%
CD19	<	0.02	cells x 10  /L
IgM	<	0.3	g/L
IgA	<	0.3	g/L

## 12 Quality of Life Analysis

Health-related quality of life and patient-reported outcomes will be assessed using questionnaires. Exploratory analyses of Quality of Life data outcomes as planned in the protocol are to be carried out by the Cambridge team. Details are outside the scope of this SAP.

### 12.1 EQ5D

EQ5D is a standardised instrument for use as a measure of health outcome, providing a simple descriptive profile and a single index value for health status.

The answers to each question will be reported at Month 4, 12, 24, 36, 42 and 48 visit, using the full analysis population. EQ5Q profiles will be summarised into a utility score for each patient using the EQ-5D-3L Index Calculator. Index scores are based on general population valuation surveys that use the TTO or VAS method for the UK (12). The following variables will be summarised in accordance with section 9:

1. Mobility
2. Self-Care
3. Usual Activities

 [https://www.economicsnetwork.ac.uk/health/EQ\\_5D\\_index\\_calculator.xls](https://www.economicsnetwork.ac.uk/health/EQ_5D_index_calculator.xls)

4. Pain/Discomfort
5. Anxiety/Depression
6. Overall index score (TTO and VAS method)

## 12.2 SF-36 questionnaire

The 36-Item Short Form Health Survey (SF-36) is a set of generic, coherent, and easily administered quality-of-life measures.

The answers to each question will be reported at Month 4, 12, 24, 36, 42 and 48 visit, using the full analysis population. The SF-36 questionnaire will be scored according to the scoring method of the RAND 36-Item Health Survey 1.0^29. All 36 individual items of the questionnaire, as well as the total score of the following domains, will be summarised in accordance with section 9:

1. Physical Functioning (PF)
2. Bodily pain (BP)
3. Role limitations due to physical health (RP)
4. Role limitations due to emotional problems (RE)
5. Energy/fatigue (EV)
6. Emotional well-being (MH)
7. Social functioning (SF)
8. General health (GH)
9. Change in Health (CH)

Additionally, two distinct, higher order summary scores will be derived from the above domains:

1. Physical Component Summary (PCS)
2. Mental Component Summary (MCS)

calculated using the subscale scoring coefficients (Table 11) and reference populations mean and standard deviation (PCS: 82.261 and 20.867; MCS: 63.7796 and 19.582) employed in PEXIVAS study.

---

 [https://www.rand.org/health/surveys\\_tools/mos/36-item-short-form/scoring.html](https://www.rand.org/health/surveys_tools/mos/36-item-short-form/scoring.html)

 The scoring procedure is explained in detail in [13, 14].

Table 11: factor score coefficients for PCS and MCS (14)

Subscale	PCS coefficients	MCS coefficients
Physical Functioning (PF)	0.418	-0.213
Role limitations due to physical health (RP)	0.334	-0.087
Bodily pain (BP)	0.366	-0.125
General health (GH)	0.222	0.036
Energy/fatigue (EV)	-0.017	0.286
Social functioning (SF)	-0.083	0.201
Role limitations due to emotional problems (RE)	-0.179	0.394
Emotional well-being (MH)	-0.200	0.444

Formulas to calculate the PCS and MCS scores:

- For the PCS:  
 $AGPHYSICO = (PF * 0.456) + (RP * 0.362) + (BP * 0.367) + (GH * 0.199) + (EV * -0.050) + (SF * -0.028) + (RE * -0.110) + (MH * -0.256)$   
 $PCS = ((AGPHYSICO - 82.261) / 20.867) * 10 + 50$
- For the MSC: :  $AGMENTCO = (PF * -0.227) + (RP * -0.102) + (BP * -0.130) + (GH * 0.036) + (EV * 0.278) + (SF * 0.272) + (RE * 0.329) + (MH * 0.460)$   
and then  $PCS = ((AGMENTCO - 63.7796) / 19.582) * 10 + 50$

### 12.3 PROMIS

The Patient-Reported Outcomes Measurement Information System assessment (PROMIS) is a set of validated health-related quality of life assessments questionnaires covering the domains that include fatigue, physical function, pain and global health.

The PROMIS questionnaire will be reported for all visits (Month 4, 8, 12, 16, 20, 24, 27, 30, 36, 42 and 48) using the ITT population. The number of sites and individuals where the PROMIS questionnaire was not administered will be noted. Individual items as well as the following totals, will be summarised in accordance with section 9:

1. Fatigue
2. Pain
3. Physical Ability
4. Patient's Global Assessment

## 13 Figures

Figure 1: CONSORT diagram.

Figure 2: Tree map of recruitment, by site and country.

Figure 3–5: Mosaic plots of relapse type by induction regimen, ANCA type by induction regimen and relapse type by ANCA type.

Figure 6: Histograms of medical history at baseline.

Figure 7: Bar chart of Organ Systems involvement at baseline.

Figure 8: Bar chart of disease status by treatment arm.

Figure 9: Histograms of BVAS/WG scores by treatment arm.

Figure 10: Histogram of CDA score at month 0 and month 4 by induction regimen (**Induction phase**).

Figure 11: Bar chart of CDA Score (grouped) at month 0 and month 4 (**Induction phase**).

Figure 12: Change in CDA Score (from baseline to month 4) (**Induction phase**).

Figure 13: Histogram of CDA score by treatment arm (**Maintenance phase**).

Figure 14: Bar chart of CDA score (grouped) by treatment arm (**Maintenance phase**).

Figure 15: Boxplot of CDA score by treatment arm (**Maintenance phase**).

Figure 16: Change in CDA Score (from month 4 to month 12) (**Maintenance phase**).

Figure 17: Change in CDA Score (from month 4 to month 24) (**Maintenance phase**).

Figure 18: Mosaic plot of treatment compliance (maintenance and follow up).

Figure 19: Bar chart of treatment compliance in maintenance phase by site.

Figure 20: Bar chart of treatment compliance in follow up phase by site.

Figure 21: Kaplan–Meier plot of relapse–free survival by treatment arm – Primary endpoint.

---

 Figure 8, 9 and 10 are similar to those found in the Induction phase report but obtained using a different scoring system for the CDA form. The figures are offered here as a comparison of the two scoring systems. The maintenance phase figures use the new scoring system exclusively.

Figure 22: Kaplan–Meier plot of relapse–free survival by treatment arm and induction regimen – Primary endpoint.

Figure 23: Kaplan–Meier plot of relapse–free survival by treatment arm and ANCA status – Primary endpoint.

Figure 24: Kaplan–Meier plot of relapse–free survival by treatment arm and relapse type – Primary endpoint

Figure 25: Forest plot of cox proportional hazards model – Primary endpoint.

Figure 26: Kaplan–Meier plot of relapse–free survival by treatment arm – Secondary endpoint.

Figure 27: Forest plot of cox proportional hazards model – Secondary endpoint.

Figure 28: Kaplan–Meier plot of relapse–free survival by treatment arm – Tertiary endpoint.

Figure 29: Forest plot of cox proportional hazards model – Tertiary endpoint.

Figure 30: Serious Adverse Events, forest plot of frequency and relative risk by treatment arm.

Figure 31: Non–serious infections, forest plot of frequency and relative risk by treatment arm.

Figure 32: Kaplan–Meier plot of SAE–free survival by treatment arm.

Figure 33–45: Boxplots by treatment arm of continuous clinical lab tests:  
Haemoglobin, Platelets, WBC, ESR, Creatinine, CRP, ALT, AST, CD19, CD19 (%), IgG, IgM, and IgA.

Figure 46–48: Stacked bar charts by treatment arm of discrete clinical lab tests:  
Anti–PR3, Anti–MPO, and ANCA status.

Figure 49: Alluvial plot of ANCA status by treatment arm, showing change from month 4 to month 24 and to month 36.

Figure 50: Bar charts of EQ–5D–5L questionnaire item's responses.

Figure 51: Boxplot of EQ–5D–5L index totals (VAS Health state, OTT utility score, and VAS utility score) by treatment arm.

Figure 52–54: Bar charts of PROMIS questionnaire item's responses (fatigue, pain, physical ability).

Figure 55: Bar chart of PROMIS questionnaire sub–totals by treatment arm.

Figure 56: Boxplots of PROMIS questionnaire sub–totals by treatment arm.

Figure 57: Boxplot of PROMIS questionnaire total score by treatment arm.

Figure 58–63: Bar charts of SF–36 questionnaire item's responses.

Figure 64: Boxplot of SF–36 questionnaire sub–totals by treatment arm.

Figure 65: Boxplot of SF-36 questionnaire PCS and MCS components by treatment arm.

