### 5.2.2 Secondary endpoints

1. Proportion of patients who maintain remission at 24 and 48 months.
2. Time to a major or second minor relapse.
3. Cumulative accrual of damage as measured by the combined damage assessment score (CDA).
4. Health-related quality of life as measured using SF-36.
5. Cumulative GC exposure.
6. Severe adverse event rate.
7. Infection (treated with intravenous or oral antibiotics) rates.

 Time measured from enrolment.

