## 11 Safety Analyses

### 11.1 Serious Adverse Events

All serious adverse events (SAE), including serious adverse drug reactions will be reported according to guidance in sections 13.4 and 13.5 of the protocol.

All Serious Adverse Events must be reported to the central trials co-ordinator or trial physician in Cambridge within 24 hours of the investigator becoming aware of the event and will be entered in a separate database. Individual SAEs will be assessed by the trial physician, and if advice is needed, this will be sought from one of the CIs, blinding them to treatment allocation. Monthly SAE listings, blinded to treatment allocation, will be reviewed by both CIs however. The Sponsor has to keep detailed records of all SAEs reported to them by the trial team.

Frequency tables for all SAEs will be reported using the safety population and stratified by both treatment arm and induction regimen as well as their interaction.

Separate tables will report:

- SAEs where date of onset occurred after randomisation
- SAEs occurring during treatment (up to 20 months after randomisation)

---

 SAEs occurring during the induction period (prior to randomisation) were reported separately, see Induction Phase SAP and report.

- SAEs occurring after treatment ended (from 20 months after randomisation onwards)

Additionally, counts of subjects and events stratified by relatedness (Unrelated/Related) will be reported, grouped by System Organ Class, High Level Group Term and Preferred Term based on the MedDRA code.

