## 11.2 Adverse Events

In addition to all SAEs, the following selected adverse events (AEs) are being collected as part of the RITAZAREM trial:

1. Infections (all episodes requiring treatment with intravenous (IV) or oral antibiotics or infections that are commonly understood to be opportunistic)
2. Occurrence of hypogammaglobulinemia (IgG <5g/l)
3. Occurrence of hypogammaglobulinemia (IgG <3g/l)
4. An adverse event that results in a change in dose of trial IMPs (rituximab, azathioprine, methotrexate or mycophenolate mofetil (MMF))
5. An adverse event that results in the addition of a relevant concomitant medication (see section 13.3.1 for list)
6. An adverse event manifested by the occurrence of a relevant laboratory abnormality (see section 13.3.2 for list)
7. New malignancies

Infections are recorded using the Infection Form and entered in the MACRO database. Frequency tables for serious and non-serious infections with date of onset occurring in the maintenance phase will be reported using the safety population and stratified by induction regime. The number of patients with newly occurring IgG < 5g/L and newly occurring IgG < 3g/L will be reported. Additionally, counts of subjects and events for non-serious infections will be reported, grouped by High Level Group Term and Preferred Term based on the MedDRA code.

Individual listings of infections are reported to the DSMB and reviewed quarterly.

New malignancies are recorded using the New Malignancy Form and entered in the MACRO database. All instances of new malignancies detected during the maintenance phase will be reported as individual listings sorted per patient by site. The following detail will be reported:

- Treatment arm
- Malignancy Detection date
- Malignancy Diagnosis date
- Malignancy Site
- Malignancy Type
- Malignancy Reoccurrence
- Malignancy Treatment (Surgery, Radiotherapy, Chemotherapy, Other)
- Malignancy Associated with SAE (Yes/No)
- Malignancy Comments

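### Secondary endpoint 7 covers all antibiotic-treated infections, but the only infection-specific relative risk is limited to non-serious ones, so no visible passage plans a between-arm estimate of the endpoint as defined

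*SAP*

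**What the plan says.** The endpoint, in the same words in Protocol 9.6.2 and SAP 5.2.2, is "Infection (treated with intravenous or oral antibiotics) rates". It has no limit by seriousness, and it is named as a rate.

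The SAP then handles infections in these places:

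- **Collection (SAP 11.2).** "Infections (all episodes requiring treatment with intravenous (IV) or oral antibiotics or infections that are commonly understood to be opportunistic". This is slightly wider than the endpoint, because opportunistic infections are included whatever the treatment.
- **Tables (SAP 11.2).** "Frequency tables for serious and non-serious infections with date of onset occurring in the maintenance phase will be reported using the safety population". The stratifier named in that sentence is induction regimen. Treatment arm comes from the general rule in SAP 9: "Summary tables will be structured with a column for each treatment arm".
- **MedDRA counts (SAP 11.2).** "counts of subjects and events for non-serious infections will be reported, grouped by High Level Group Term and Preferred Term".
- **Figures (SAP 13).** The infection figure is "Figure 31: Non–serious infections, forest plot of frequency and relative risk by treatment arm", so its relative risk is for non-serious infections only. Its companion is "Figure 30: Serious Adverse Events, forest plot of frequency and relative risk by treatment arm".
- **Serious adverse events (SAP 11.1).** Subject and event counts are "grouped by System Organ Class, High Level Group Term and Preferred Term based on the MedDRA code".
- **Models for secondary outcomes (SAP 10.2).** Only two relapse outcomes are listed, and infection is not one of them.

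**The concern.** A pre-specified secondary safety endpoint should have one planned comparison that matches its definition. Here the infection-specific comparison is made on a subset, and the subset is chosen by how severe the infection turned out to be.

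Under Protocol 13.1.4, admission to hospital makes an event serious. An infection that leads to admission therefore drops out of Figure 31. Severity may itself be affected by treatment, so the restriction can act differently in the two arms: an arm in which more infections become serious loses more of them from the figure.

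The Protocol makes the long-term safety of rituximab a secondary objective (9.5.2) and collects all infections as events of interest (13.2). A reader looking for the effect on treated infections would find Figure 31, which answers a different question.

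**Working it through.** **Step 1. Endpoint against planned outputs.**

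| Output | Infections covered | Between-arm estimate? |
|---|---|---|
| Endpoint 7 (Protocol 9.6.2, SAP 5.2.2) | all treated, as a rate | this is what is needed |
| SAP 10.2 models | none | no |
| SAP 11.2 frequency tables | serious and non-serious | no; counts, by arm under the SAP 9 default |
| SAP 11.2 MedDRA counts | non-serious | no; counts |
| SAP 13, Figure 31 | non-serious | relative risk |
| SAP 11.1 counts | serious, as part of all SAEs | no; counts |
| SAP 13, Figure 30 | serious, as part of all SAEs; MedDRA level not stated | relative risk |

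No row gives a relative risk, rate ratio or difference for serious and non-serious treated infections together, and none gives a rate per patient-time. This result needs no assumption about event rates.

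**Step 2. Can the two halves be added afterwards?** Counts of patients cannot, because one patient may have both kinds of infection. Counts of events can, approximately. The match is not exact, because an infection counted as an SAE need not have been given antibiotics, and because SAEs are held in a separate database (SAP 11.1) while Infection Forms are in MACRO (SAP 11.2).

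**Step 3. How far can Figure 31 depart from the endpoint?** The documents give no infection rates, so there is no figure to reproduce and every count below is an assumption. Only the 80 per arm comes from the plan (160 randomised 1:1).

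Let A be the patients in an arm with any treated infection, S those with a serious one, and o the share of S who also have a non-serious one (taken as equal in both arms). The patients counted in Figure 31 are then

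N = A − S × (1 − o).

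Take A = 44 (rituximab) v 40 (azathioprine). The relative risk for any treated infection is 44/40 = 1.10 (95% CI 0.82 to 1.48). With S = 16 v 5, the relative risk for serious infection is 3.20 (1.23 to 8.32), and:

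| Share with both kinds (o) | N, rituximab v azathioprine | Figure 31 relative risk |
|---|---|---|
| 0% | 28 v 35 | 0.80 (0.54 to 1.18) |
| 50% | 36 v 37.5 | 0.96 |
| 75% | 40 v 38.75 | 1.03 |
| 100% | 44 v 40 | 1.10 |

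The range of the Figure 31 relative risk, as o runs from 0% to 100%, for other assumed numbers of patients with a serious infection:

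- 5 v 5: 1.11 to 1.10, so no material distortion
- 10 v 5: 0.97 to 1.10
- 20 v 5: 0.69 to 1.10

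**Step 4. When does the direction reverse?** Figure 31 falls below 1 when 44 − S_R(1 − o) < 40 − S_A(1 − o), that is, when (1 − o) > 4/(S_R − S_A). For 16 v 5 this is 4/11 = 0.36, so o must be below 64%. For 10 v 5 it is 4/5 = 0.80, so o must be below 20%. For 20 v 5 it is 4/15 = 0.27, so o must be below 73%. With equal numbers of serious infections there is no reversal.

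**The case against.** A reader might infer that serious infections are never compared between arms, or that the safety report could make an arm with more severe infections look safer. The documents do not support either reading.

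- Figure 30 plans relative risks by arm for SAEs, and serious infections are SAEs. The SAP does not say at which MedDRA level the figure is drawn, so a separate infection row is likely but not certain.
- SAP 11.2 itself tabulates serious infections, and the SAP 9 layout gives each arm a column. An imbalance such as the assumed 16 v 5 would show there.
- Figure 31 is labelled as non-serious. Nothing in the SAP offers it as the estimate for endpoint 7.
- The distortion needs both an imbalance in serious infections and limited overlap within patients. The Protocol's own pilot cohort (7.3.1) reported no increased risk of serious infections with six-monthly rituximab.
- SAP 10.2 calls its secondary analyses exploratory, and the full table list (SAP 17) is in a file outside the published documents.

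All of this stands, and it limits the possible harm to Figure 31 read on its own. It does not supply the missing estimate. Serious infections among SAEs are one part of the endpoint, tables of counts carry no effect size or interval, and a reader should not have to assemble a pre-specified endpoint from two sources.

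**Conclusion.** The point holds as a mismatch between a secondary endpoint and its planned analysis. On the visible text, endpoint 7 has no between-arm estimate as defined, and the one infection-specific relative risk is taken on a subset selected by outcome severity.

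An excess of serious infections would probably still be visible elsewhere in the report. How far Figure 31 would differ from the endpoint is unknown. The 0.80 to 1.10 range against 1.10 rests wholly on assumed counts, on equal overlap in the two arms, and on Figure 31 counting patients rather than events, which the SAP does not state. The primary analysis is not affected. The change should be made because the endpoint is pre-specified and the data are already collected.

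**What to change.** In SAP 11.2 and Section 13:

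1. Add a comparison by randomised arm of all infections meeting endpoint 7, serious and non-serious together. Give events per patient-year with a rate ratio and 95% CI. A rate is needed because follow-up runs from 36 to 48 months from entry (Protocol 12.4), or 32 to 44 months after the month 4 randomisation. Repeated infections in one patient should be allowed for in the interval.
2. Beside it, give the number of patients with at least one such infection, each counted once. This is a proportion and does not replace the rate.
3. Extend the MedDRA counts to all infections, and show serious and non-serious infections as components. Figure 31 may stay as a breakdown.
4. Name treatment arm explicitly in the infection tables, and state the MedDRA level of Figure 30.
5. State the time window. SAP 9.1.1 ends the maintenance phase at month 24, whereas SAP 4.2 and 6.4 use the term to include follow-up.

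The cost is SAP wording, a modest re-run, and reconciling the Infection Form data in MACRO with the separate SAE database. That the Infection Form identifies serious episodes is inferred from the tables planned in 11.2 and should be confirmed. No new data collection appears to be needed.
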